7.3.3. Post operative recovery phase (following discharge)

- Grade 2 events

7.3.4. During systemic chemotherapy administration

- Grade 1 and 2 events that are listed in the package insert of any of the agents
- Grade 3 events that are listed in the package insert of any of the agents and do NOT require hospitalization. Events that initiate dose reduction will be captured as described in Section 7.1.1

Note: Events that result in a hospitalization for convenience will not be reported.

7.3.5. Concomitant medications:

Only those medications that the patient is taking at baseline on a routine basis or medications that cause an AE will be captured in C3D. {Thus onetime medications, PRN medications, and medications given to treat adverse events will not be captured in C3D.}

7.4. NCI-IRB REPORTING

7.4.1. NCI-IRB Expedited Reporting of Adverse Events, Unanticipated Problems, and Deaths

The Protocol PI will report to the NCI-IRB:

- All unexpected serious adverse events that are possibly, probably, or definitely related to the research
- All deaths, except deaths due to progressive disease
- All Protocol Violations or Deviations
- All Unanticipated Problems

Reports must be received by the NCI-IRB within 7 working days of PI awareness via iRIS.

7.4.2. NCI-IRB Requirements for PI Reporting of Adverse Events at Continuing Review

The protocol PI will report to the NCI-IRB:

- All Grade 2 unexpected events that are possibly, probably or definitely related to the research;
- All Grade 3 and 4 events that are possibly, probably or definitely related to the research;
- All Grade 5 events regardless of attribution;
- All Serious Events regardless of attribution.

NOTE: Grade 1 events are not required to be reported

8. Pharmaceutical Information:

8.1. Oxaliplatin

8.1.1. Source:

Oxaliplatin is commercially available (manufacturer: Sanofi-Winthrop, France) and will be purchased from commercial sources by the NIH Clinical Center Pharmacy Department.

8.1.2. Toxicities:

Predominant dose-limiting toxicity: sensory peripheral neuropathy. Fifty-six percent of patients with this combined therapy experienced an acute, reversible primarily peripheral sensory neuropathy that is of early onset, occurring within hours or one or two days of dosing, that resolves within 14 days, and that frequently recurs with further dosing. The symptoms may be precipitated or exacerbated by exposure to cold temperature or cold objects and they usually present as transient paresthesia, dysesthesia and hypoesthesia in the hands, feet, perioral area or throat. Jaw spasm, abnormal tongue sensation, dysarthria, eye pain, and a feeling of chest pressure have also been observed. An acute syndrome of pharyngolaryngeal dysesthesia seen in 1-2 % of patients is characterized by subjective sensations of dysphagia or dyspnea, with laryngospasm or bronchospasm. In 48% of

patients receiving this combination, a persistent (> 14 days), primarily peripheral, sensory neuropathy that is usually characterized by paresthesias, dysesthesias, hypoesthesia, but may also include deficits in proprioception that can interfere with daily activities (e.g., writing, buttoning, swallowing, and difficulty walking from impaired proprioception) has occurred. Oxaliplatin has been associated with pulmonary fibrosis (0.7% of study patients), which may be fatal. If patients experience unexplained respiratory symptoms such as non-productive cough, dyspnea, crackles, or radiological pulmonary infiltrates, the agent should be discontinued until further pulmonary investigation excludes pulmonary fibrosis or interstitial lung disease. Other effects: nausea, vomiting, diarrhea, mucositis, transaminase elevations, and alopecia. Myelosuppression is minimal with the agent alone but may be significant when given in combination with 5-FU/LV; severe nephrotoxicity not reported. Extravasation of oxaliplatin may result in local pain and inflammation that may be severe and lead to complications, including necrosis. Injection site reaction, including redness, swelling and pain have been reported.

8.1.3. Formulation and Preparation:

Oxaliplatin is supplied in clear, glass, single-use vials with gray elastomeric stoppers and aluminum flip-off seals containing 50 mg or 100 mg as a sterile, preservative-free lyophilized powder for reconstitution, containing lactose monohydrate as an inactive ingredient (450mg or 900 mg respectively). For IV administration, the appropriate dose is reconstituted in a parenteral solution of 250 mL of 5% Dextrose Injection, USP (D5W). For CHPP administration, Oxaliplatin 460 mg/m² is diluted in 2.0 L/m² of D5W and administered via the perfusion circuit. Reconstitution of final dilution must never be performed with a sodium chloride solution or other chloride-containing solutions.

8.1.4. Stability/Storage:

Oxaliplatin is stable when stored under normal lighting conditions at room temperature of 25°C (77°F). After reconstitution in the original vial, the solution may be stored up to 24 hours under refrigeration (2-8°C (36-46°F)). After final dilution with 5% Dextrose Injection, USP, the shelf life is 6 hours at room temperature [20-25°C (68-77°F)] or up to 24 hour under refrigeration [2-8°C (26-46°F)]. Oxaliplatin is not light sensitive.

8.1.5. Administration:

Oxaliplatin will be administered in a 250 mL solution of 5% Dextrose Injection, USP (D5W) as a 2 hour infusion on day one of each cycle concurrently with leucovorin in different IV lines. Oxaliplatin is incompatible in solution with alkaline medications or media and must not be mixed with these or administered simultaneously through one infusion line. The infusion line should be flushed with D5W prior to administration of any concomitant medication.

8.2. Leucovorin Calcium (Injection)

8.2.1. Source:

Leucovorin calcium injection will be purchased from commercial sources by the NIH Clinical Center Pharmacy Department.

8.2.2. Toxicity:

Allergic sensitization has been reported following both oral and parenteral administrations of folinic acid.

8.2.3. Formulation and Storage:

Leucovorin calcium is supplied as 350 mg/vial dry powder and will be reconstituted with sterile water for injection, USP, to a concentration of 20mg/ml. Intact vials of leucovorin need to be stored at controlled room temperature (25 degrees C) and protected from light.

8.2.4. Stability:

Leucovorin has been administered extensively with FUDR and dexamethasone as a 2 week intra-arterial infusion in patients with colorectal cancer and loses less than 10% of its activity in solution with these agents at more than 60 days of incubation.

8.2.5. Administration Procedures:

Leucovorin will also be administered on day 1 of each cycle at a dose of 200 mg/m² intravenously over 2 hours concomitant with oxaliplatin. Doses will be based on actual body weight if patient's weight is within 20% of the ideal body weight. If the patient's weight is 20% above or below the ideal body weight, then ideal body weight will be used to calculate systemic chemotherapy doses. Leucovorin will be diluted in 5% Dextrose Injection, USP (D5W).

8.3. 5-Fluorouracil

8.3.1. Source:

It will be purchased commercially by the NIH Clinical Center Pharmacy Department.

8.3.2. Toxicities:

The most common adverse reactions include stomatitis, esophagopharyngitis, diarrhea, anorexia, nausea, emesis, dermatitis, and alopecia. Hand-foot syndrome (palmar-plantar erythrodysesthesia) has been observed with 5-FU administration. Bone marrow suppression may occur at high doses with the lowest counts expected between the 9th and 14th day of treatment. Leukopenia is the most common hematologic toxicity associated with fluorouracil (5-FU) with the nadir typically between 9 and 14 days after treatment. The white blood cell count usually returns to normal after stopping treatment. Ischemic chest pain and myocardial ischemia or signs of electrocardiogram changes may occur with fluorouracil administration. Onset of chest pain in many cases occurs within hours of receiving a second or third dose but may be associated with the first dose. Anginal attacks often recur upon rechallenge, but may or may not be prevented with vasodilators such as nitrates or calcium channel blockers. Death has occurred secondary to cardiogenic shock. Most commonly, these effects occur when the drug is administered as a continuous infusion and within several hours from the start of the infusion. Patients with pre-existing coronary artery disease (CAD) appear to be at greater risk; however, most reported cases are in those with no previous history of CAD. Neurological effects reported by the manufacturer include nystagmus, headache, disorientation and euphoria. Of 25 patients receiving low-dose leucovorin (20 mg/m²) and fluorouracil (425 to 600 mg/m²), 15 (65%) developed hypocalcemia, and two each had tetany or hiccups.

Calcium levels should be monitored in patients receiving this regimen, and calcium supplementation should be provided if calcium levels are low. The manufacturer reports that visual changes and photophobia have occurred with 5-fluorouracil use.

8.3.3. Formulation and Preparation:

5-FU (Fluorouracil) is supplied as a sterile, nonpyrogenic injectable solution for administration. Each 10-cc contains 500 mg in a colorless to faint yellow aqueous solution. The pH is adjusted to 9.2 with sodium hydroxide.

8.3.4. Stability/Storage:

Fluorouracil solutions should be stored at room temperature and protected from light. Solutions may discolor slightly but potency and safety are not adversely affected. Any precipitate which forms may be resolubilized by heating and agitation. The stability of aqueous fluorouracil 50 mg/mL was studied in portable infusion pumps under simulated infusion conditions. The drug was found to be stable for 7 days at 37 °C. Fluorouracil solution maintained 98% to 100% potency over 48 hours after dilution and storage in syringes or ethylene vinyl acetate infusion-pump reservoirs.

8.3.5. Administration:

Intravenous administration (Intra-operative)

Each 10 ml ampoule contains 500 mg of fluorouracil, and the appropriate amount is diluted in a parenteral solution of 5% Dextrose Injection, USP (D5W). 5-FU will be administered on days 1 and 2 of each cycle of systemic chemotherapy at a dose of 3200 mg/m² via continuous intravenous infusion over 48 hours. Doses will be based on actual body weight if patient's weight is within 20% of the ideal body weight. If the patient's weight is 20% above or below the ideal body weight, then ideal body weight will be used to calculate systemic chemotherapy doses. See Section 3.2.2 for the calculation for ideal body weight.

8.4. Irinotecan

8.4.1. Source:

Irinotecan is commercially available and will be purchased by the CC Pharmacy Department.

8.4.2. Adverse effects:

The most clinically significant adverse events for patients receiving irinotecan-based therapy were diarrhea, nausea, vomiting, neutropenia, increased bilirubin, interstitial lung disease, and alopecia. Irinotecan can induce both early and late forms of diarrhea that appear to be mediated by different mechanisms. Both forms of diarrhea may be severe. Early diarrhea (occurring during or shortly after infusion of irinotecan) may be accompanied by cholinergic symptoms of rhinitis, increased salivation, miosis, lacrimation, diaphoresis, flushing, and intestinal hyperperistalsis that can cause abdominal cramping. Early diarrhea and other cholinergic symptoms may be prevented or ameliorated by atropine late diarrhea (generally occurring more than 24 hours after administration of irinotecan) can be life threatening since it may be prolonged and may lead to dehydration, electrolyte imbalance, or sepsis. Late diarrhea should be treated

promptly with loperamide. Patients with diarrhea should be carefully monitored and given fluid, and electrolyte replacement if they become dehydrated, or antibiotic therapy if they develop ileus, fever, or severe neutropenia.

8.4.3. Formulation and preparation:

Irinotecan is supplied as 20 mg/mL solution (on the basis of the trihydrate salt); 45 mg sorbitol; and 0.9 mg lactic acid in single-dose amber 2mL (40 mg) and 5mL (100 mg) vials. When necessary, pH has been adjusted to 3.5 (range, 3.0 to 3.8) with sodium hydroxide or hydrochloric acid. Solutions should be diluted in 5% Dextrose Injection, USP, (preferred) or 0.9% Sodium Chloride Injection, USP, to a final concentration range of 0.12 to 2.8 mg/mL using 100 to 500 mL of 5% Dextrose Injection, USP.

8.4.4. Stability/Storage:

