3.5.3. Treatment Modifications FOLFOXIRI

Treatment will be continued for up to 12 cycles (4 cycles = 1 course) unless one of the following events occur: disease progression, unacceptable adverse effects, or withdrawal of patient consent. Dose modification will be based on toxicity profiles and adverse effects based upon the National Cancer Institute Common Terminology Criteria for Adverse Events (CTCAE version 3.0).

The dose levels for oxaliplatin, irinotecan, leucovorin and 5-FU are noted above; the dose modification table is attached as Appendix 4.

NOTE: Patients for whom peripheral neuropathy would pose significant hardship (e.g., musicians, jewelers, dentists) may receive the standard FOLFIRI regimen as noted below.

FOLFIRI			
Agent	Starting Dose	Dose level -1 (25% reduction)	Dose level -2 - 50% reduction
Irinotecan	180 mg/ m ² IV	150 / m ² IV	120 /m ² IV
Leucovorin	200 mg/m ² IV	200 m ² IV	200 mg/m ² IV
5-FU bolus	400 mg/m ² IV	320 mg/m ² IV	240 mg/m ² IV
5-FU infusion (over 46 hours)	2400 mg/m ² CIV	2000 mg/m ² CIV	1600 mg/m ² CIV

Day 1: Irinotecan will be administered IV over 90 minutes followed by leucovorin IV over 2 hours followed by 5-FU bolus injection, followed by 5-FU given via continuous infusion (CIV) over 46 hours. Dose reductions will follow appendix 4; all evaluations will follow the same schedule as outlined for FOLFOXIRI.

3.6. Treatment Evaluation During Chemotherapy:

- Laboratory evaluation weekly or according to the standards of the treating physician, to include: CBC with differential and Chem 20: (Sodium (Na), Potassium (K), Chloride (Cl), Total CO₂ (bicarbonate), Creatinine, Glucose, Urea nitrogen (BUN), Albumin, Calcium total, Magnesium total (Mg), Inorganic Phosphorus, Alkaline Phosphatase, ALT/GPT, AST/GOT, Total Bilirubin, Direct Bilirubin, LD, Total Protein, Total CK, Uric Acid).
- Physical examination and toxicity assessment every 2 weeks or according to the standards of the treating physician

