Appendix 4 Dose Modification FOLFOXIRI

event-grade	irinotecan	oxaliplatin	SFU
neutropenia**			
grade 1	maintain dose level	maintain dose level	maintain dose level
grade 2	maintain dose level	maintain dose level	maintain dose level
grade 3	maintain dose level	maintain dose level	maintain dose level
grade 4> 5 days	↓ 1 dose level	↓ 1 dose level	maintain dose level
febrile neutropenia grade 4	↓ 1 dose level	↓ 1 dose level	maintain dose level
thrombocytopenia**			
grade 1	maintain dose level	maintain dose level	maintain dose level
grade 2	maintain dose level	maintain dose level	maintain dose level
grade 3	↓ 1 dose level	↓ 1 dose level	maintain dose level
grade 4	↓ 1 dose level	↓ 1 dose level	maintain dose level
anemia			
grade 1	maintain dose level	maintain dose level	maintain dose level
grade 2	maintain dose level	maintain dose level	maintain dose level
grade 3	maintain dose level	maintain dose level	maintain dose level
grade 4	maintain dose level	maintain dose level	maintain dose level
diarrhea**			
2-3 stools/day > baseline	maintain dose level	maintain dose level	maintain dose level
4-6 stools/day > baseline	maintain dose level	maintain dose level	maintain dose level
7-9 stools/day > baseline	↓ 1 dose level	maintain dose level	↓ 1 dose level
≥ 10 stools/day > baseline	↓ 2 dose levels	maintain dose level	↓ 2 dose levels
mucositis/stomatitis**			
grade 1	maintain dose level	maintain dose level	maintain dose level
grade 2	maintain dose level	maintain dose level	maintain dose level
grade 3	maintain dose level	maintain dose level	↓ 1 dose level
grade 4	maintain dose level	maintain dose level	↓ 2 dose levels
hand foot syndrome			
grade 3-4	maintain dose level	maintain dose level	discontinue
other non-heme toxicities* & **			
grade 1	maintain dose level	maintain dose level	maintain dose level
grade 2	maintain dose level	maintain dose level	maintain dose level
grade 3	↓ 1 dose level	↓ 1 dose level	↓ 1 dose level
grade 4	↓ 2 dose levels	↓ 2 dose levels	↓ 2 dose levels
neuropathy			
grade 1: resolves - does not interfere with functioning	maintain dose level	maintain dose level	maintain dose level
grade 2: interferes with functioning but not daily activities and does not resolve	maintain dose level	maintain dose level	maintain dose level
grade 3: pain or functional impairment that interferes with daily activities	maintain dose level	discontinue	maintain dose level

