grade 4: persistent impairment that is disabling or life-threatening.	maintain dose level	discontinue	maintain dose level

*excludes alopecia, anorexia, asthenia, lab toxicities

**The next dose should be delayed until: WBC >3000, neutrophils >1000 - platelets > 100,000

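### The plan names interstitial lung disease as a significant irinotecan toxicity but specifies no irinotecan hold while it is investigated; its only pulmonary hold covers oxaliplatin

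*Combined protocol and SAP*

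**What the plan says.** Section 8.4.2 (Irinotecan, adverse effects) lists ILD among seven leading toxicities: "The most clinically significant adverse events for patients receiving irinotecan-based therapy were diarrhea, nausea, vomiting, neutropenia, increased bilirubin, interstitial lung disease, and alopecia". The management advice that follows deals with diarrhea and cholinergic symptoms. Nothing is said about what to do for the lung.

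Section 8.1.2 (Oxaliplatin, toxicities) reports pulmonary fibrosis in 0.7% of study patients, notes that it may be fatal, and says that for unexplained respiratory symptoms or infiltrates "the agent should be discontinued until further pulmonary investigation excludes pulmonary fibrosis or interstitial lung disease". The agent meant there is oxaliplatin.

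Appendix 4 (dose modification) has no pulmonary row. Its catch-all row, "other non-heme toxicities", carries two footnotes. One "excludes alopecia, anorexia, asthenia, lab toxicities"; ILD is not among these exemptions. The other is the delay rule: "The next dose should be delayed until: WBC >3000, neutrophils >1000 - platelets > 100,000".

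Section 3.5.3 says that patients for whom neuropathy would be a particular hardship "may receive the standard FOLFIRI regimen as noted below". That regimen contains irinotecan and no oxaliplatin. It uses the same table: "Dose reductions will follow appendix 4; all evaluations will follow the same schedule as outlined for FOLFOXIRI".

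**The concern.** The authors recognised lung injury as a hazard of two drugs given on the same day, and wrote a hold for one of them. On FOLFOXIRI, a patient with new dyspnea and infiltrates has oxaliplatin held under 8.1.2, while the only table entry that fits the event keeps irinotecan going. On FOLFIRI, the oxaliplatin hold has no drug to act on.

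What is at stake is patient safety during the period when ILD is suspected but not yet confirmed. Much of the chemotherapy may be given by local oncologists (section 3.5.1), so the written table is the common instruction across treating sites.

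**Working it through.** The plan states no figure to reproduce here. The check sets the sections side by side and reads off the doses.

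**1. Where each event named in 8.4.2 lands in Appendix 4**

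| Event | Place in Appendix 4 |
|---|---|
| Diarrhea | own row |
| Neutropenia | own row |
| Alopecia | exempt by footnote |
| Increased bilirubin | exempt, read as a laboratory toxicity |
| Nausea | catch-all row |
| Vomiting | catch-all row |
| ILD | catch-all row |

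That makes 2 with their own row, 2 exempt and 3 in the catch-all, 7 in all. ILD is dosed by the same rule as vomiting.

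**2. What the catch-all row does to irinotecan.** It maintains the dose at grades 1 and 2, lowers it one level at grade 3 and two levels at grade 4. With the dose levels printed in 3.5.2 and 3.5.3 (mg/m²):

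| Grade | FOLFOXIRI | Share of start | FOLFIRI | Share of start |
|---|---|---|---|---|
| 1-2 | 165 | 100% | 180 | 100% |
| 3 | 123 | 123/165 = 75% | 150 | 150/180 = 83% |
| 4 | 82 | 82/165 = 50% | 120 | 120/180 = 67% |

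The irinotecan entry is not zero at any grade. The delay footnote on this row depends on white cells, neutrophils and platelets, so a patient with normal counts meets no delay on account of the lung.

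**3. What 8.1.2 does in the same patient.** Oxaliplatin is withheld, whatever the grade, until the lung work-up excludes fibrosis or ILD. The two rules give different answers for two drugs that the plan itself links to lung injury.

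**4. Who is outside the oxaliplatin hold.** Two groups receive irinotecan without oxaliplatin:
- patients on FOLFIRI under 3.5.3;
- patients on FOLFOXIRI whose neuropathy reaches grade 3, defined in Appendix 4 as "pain or functional impairment that interferes with daily activities", or grade 4. There the table discontinues oxaliplatin and maintains irinotecan.

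The documents size neither group.

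**5. Whether the table can express a stop.** It can. It uses a discontinue entry for oxaliplatin in grade 3-4 neuropathy and for 5-FU in grade 3-4 hand-foot syndrome. It has no such entry for irinotecan.

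**The case against.** The strongest reply is that Appendix 4 sets dose levels for patients fit to continue, and that other sections decide who stops. Section 3.5.3 ends treatment for unacceptable adverse effects. Section 3.8 adds unacceptable toxicity and the physician's judgement of the patient's interest. Section 3.5.1 defers to each institution's chemotherapy policies. The catch-all row never discontinues any drug: read literally, it would only reduce 5-FU after grade 4 cardiac ischemia, although 8.3.2 reports deaths from cardiogenic shock. On FOLFOXIRI, 8.1.2 already sends the symptomatic patient for lung investigation. The entry criteria also exclude obstructive or restrictive pulmonary disease.

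Much of this stands. A reader might infer that the plan compels irinotecan to continue through confirmed ILD, or that FOLFIRI patients cannot be stopped. The documents do not support either reading, because 3.5.3 and 3.8 are written stop rules for both regimens. A reader might also want a count of patients harmed. The plan gives no rate for irinotecan ILD, and even a rate would count cases of ILD, not cases where an oncologist kept dosing because of the table.

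What the reply does not supply is a hold. The general rules are undefined and discretionary, and they end treatment; none directs that irinotecan be withheld while ILD is investigated. At grades 1-2, when early ILD would be under suspicion, the specific table says to maintain the dose. The content of the local policies is not given. Section 8.1.2 shows that, for oxaliplatin, the authors did not leave this situation to general discretion.

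**Conclusion.** The point holds as a safety-rule inconsistency. The plan specifies no irinotecan hold during the work-up of suspected ILD, and the row that applies leaves irinotecan at 100% of the starting dose at grades 1-2 and at 50% to 83% at grades 3-4, depending on regimen and grade. No specified pulmonary hold reaches patients receiving irinotecan without oxaliplatin.

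This rests on two readings: that the agent in 8.1.2 is oxaliplatin alone, and that ILD belongs to the catch-all row because it has no row of its own and no exemption. Both follow from the text. It is not certain harm, since a clinician can stop treatment within the plan. Sample size, power and the overall survival analysis are untouched. The correction is worth making because the right trigger already stands in the plan and only needs extending to the second drug.

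**What to change.** Add one row to Appendix 4, stated to apply to FOLFOXIRI and FOLFIRI, along these lines:

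> Respiratory symptoms without another explanation (such as dry cough, breathlessness or crackles), or lung infiltrates on imaging, any grade: hold irinotecan, and oxaliplatin if given (see 8.1.2), until pulmonary investigation excludes fibrosis and ILD. Discontinue both permanently if either is confirmed. For these two drugs this row overrides the other non-heme row.

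Add a matching sentence to 8.4.2. An inconclusive work-up then leaves the hold in place, as 8.1.2 already does for oxaliplatin; only confirmation makes it permanent. 5-FU stays on its existing row, since the documents do not link it to lung injury.

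The cost is a short amendment, sent to the treating oncologists, and a few irinotecan doses held for symptoms that prove benign. Those holds may not fall evenly between arms, because thoracotomy for lung metastases is part of GYMS treatment. They should therefore be recorded with their reason: the effect of surgery on chemotherapy dosing and duration is a secondary objective, and 7.2.1 names dose reductions but not holds. No visits or patients are added.
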